8.3 Severity

The intensity of adverse events will be graded by the Investigator on a 3-point scale as indicated on the CRF. The intensity of an adverse event is defined as follows:

- **Mild:** Discomfort noticed, but no disruption to daily activity
- **Moderate:** Discomfort sufficient to reduce or affect normal daily activity
- **Severe:** Inability to work or perform normal daily activity

8.4 Collection of Adverse Events

The Investigator will periodically assess patients for the occurrence of adverse events. To avoid bias in eliciting adverse events, patients should be asked the following non-leading question: "How are you feeling?" All adverse events (serious and non-serious) reported by the patient will be followed until the event has resolved or has stabilized.

8.4.1 Collection and Reporting of Nonserious Adverse Events

Nonserious adverse events will be collected from study drug initiation through to 48 hours following PCI or hospital discharge, whichever comes first on the CRF but will not require urgent expedited reporting.

8.4.2 Collection and Reporting of Serious Adverse Events

Serious adverse events (including serious bleeding events) will be collected on the CRF. The Investigator is responsible for following all SAEs until the event has resolved or has stabilized.

In the event of an SAE, or in the event of death due to any cause, immediately (within 24 hours) the SAE form is to be completed and submitted to:

Name: [name]
Title: Clinical Safety Officer
[contact]
Email: [contact]
[contact]

If details of the event are not known submit the SAE form within 24 hours and update the information as it becomes available.

8.4.3 Collection and Reporting of Endpoints

Endpoints will be collected on the case report form from study drug administration through 48 hours following PCI or hospital discharge, whichever comes first. Any coronary ischemic or anginal event will be collected on the CRF but will not require urgent/expedited reporting. Endpoints will not be reported as SAEs.

8.5 Submission of Follow-up Data

The Investigator is responsible for following all SAEs until the event has resolved or has stabilized. The Sponsor's Safety Surveillance Contact will follow all SAEs with outcomes pending until the last patient enrolled has completed the study.

8.6 Ethics Committee SAE Reporting

The Investigator will be responsible for reporting adverse events to the Independent Review Board (IRB) and their local regulatory authorities in accordance with their local guidelines.

9.0 STATISTICAL CONSIDERATIONS

This section summarizes the statistical aspects of the protocol. A final statistical analysis plan (SAP), which will provide detailed descriptions of the statistical methodology and mock tables, listings and figures (TLFs), will be completed prior to any blinded sample size reassessment or final analysis.

9.1 Study Design

A randomized, multicenter, open-label study comparing tirofiban I.V. bolus injection followed by a maintenance infusion for the duration of the PCI procedure plus a minimum of one hour and up to a maximum of two hours post-PCI versus label-dosing eptifibatide. Patients were randomized to tirofiban or eptifibatide using a 1:1 allocation ratio. After 159 patients were randomized, a 1:1:1 randomization was initiated, randomizing patients to short tirofiban, eptifibatide or long tirofiban. Randomization in the long tirofiban arm is completed, changing the allocation ratio back to 1:1. Patients are mandated to stay a minimum of 18 hours following PCI.

Physician-directed standard background therapies will include dual oral antiplatelet therapy with aspirin and an approved oral P2Y₁₂ antagonist as well as antithrombotic therapy with unfractionated heparin. Physician-directed P2Y₁₂ antagonist therapy and choice of femoral or radial access site must be pre-specified prior to randomization.

The first 159 patients were randomized to the following two treatment arms on a 1:1 basis:

1. Tirofiban (25 µg/kg bolus followed by a 0.15 µg/kg/min infusion for the duration of the PCI procedure plus a minimum of one hour and up to a maximum of two hours post-PCI).
2. Eptifibatide (180 µg/kg bolus followed by a 2.0 µg/kg/min infusion for 18 hours post-PCI [minimum 12 hours mandated], with a second 180 µg/kg bolus 10 min after the first).

The three treatment arms for enrollment after the 159th patient were:

1. Short Tirofiban (25 µg/kg bolus followed by a 0.15 µg/kg/min infusion for the duration of the PCI procedure plus a minimum of one hour and up to a maximum of two hours post-PCI).
2. Eptifibatide (180 µg/kg bolus followed by a 2.0 µg/kg/min infusion for 18 hours post-PCI [minimum 12 hours mandated], with a second 180 µg/kg bolus 10 min after the first).
3. Long Tirofiban (25 µg/kg bolus followed by a 0.15 µg/kg/min infusion for 18 hours post-PCI) [minimum 12 hours mandated].

Enrolment in the Long Tirofiban arm is completed. Enrolment continues in the Short Tirofiban and Eptifibatide arms as outlined above.

Approximately 550 patients will be enrolled into the study.

9.2 Statistical Alternative Hypothesis (Ha)

The first primary test is that short tirofiban is non-inferior to eptifibatide for death, PPM, uTVR or REPLACE-2 Major bleeding within 48 hours following PCI or hospital discharge, whichever comes first. The original non-inferiority margin was 12.4% (with an expected pooled rate of 32.5%), but based on the higher observed pooled event rate of 51% after 159 randomized patients, the non-inferiority margin was revised to be 19.1% in order to maintain the same relative margin (i.e. $12.4\% / 32.5\% = 19.1\% / 51\% = 0.38$) For the co-primary tests, the same non-inferiority margin (19.1%) will be used.

9.3 Study Endpoints, Covariates, and Subgroups

9.3.1 Primary Endpoint and Associated Tests

First primary test: A short tirofiban regimen of a high-dose bolus plus a shortened infusion duration is non-inferior to label-dosing eptifibatide among patients undergoing PCI with respect to death, PPM, uTVR or major bleeding within 48 hours following PCI or hospital discharge, whichever comes first. Co-primary tests: (i) a short tirofiban regimen of a high-dose bolus plus a 1-2 hour infusion post procedure is non-inferior to a long tirofiban regimen of a high-dose bolus plus a 12-18 hour infusion with respect to death, PPM, uTVR or major bleeding within 48 hours following PCI or hospital discharge, whichever comes first, and (ii) a long tirofiban regimen of a high-dose bolus plus a 12-18 hour infusion is non-inferior to label-dosing eptifibatide with respect to death, PPM, uTVR or major bleeding within 48 hours following PCI or hospital discharge, whichever comes first. No adjustments for multiple testing will be made.

9.3.2 Secondary Endpoint and Associated Tests

First secondary test: A short tirofiban regimen of a high-dose bolus plus a shortened infusion duration is non-inferior to label-dosing eptifibatide among patients undergoing PCI with respect to the following list:

- death, PPM or uTVR within 48 hours following PCI or hospital discharge, whichever comes first
- PPM within 48 hours following PCI or hospital discharge, whichever comes first
- uTVR within 48 hours following PCI or hospital discharge, whichever comes first
- death within 48 hours following PCI or hospital discharge, whichever comes first
- death, PPM, uTVR or major bleeding within 48 hours following PCI or hospital discharge, whichever comes first, where PPM is defined as at least one troponin elevation of ≥ 10 times the upper limit of normal AND at least 20% of greater than the baseline troponin value, per the troponin Local Laboratory within 48 hours following PCI or hospital discharge, whichever comes first (a non-inferiority margin of 12.4% will be used for the short tirofiban versus eptifibatide comparison)
- at least one troponin elevation of ≥ 10 times the upper limit of normal AND at least 20% of greater than the baseline troponin value, per the troponin Local Laboratory, within 48 hours following PCI or hospital discharge, whichever comes first (a non-inferiority margin of 12.4% will be used for the short tirofiban versus eptifibatide comparison)
- at least one troponin elevation of ≥ 20 times the upper limit of normal AND at least 20% of greater than the baseline troponin value, per the troponin Local Laboratory, within 48 hours following PCI or hospital discharge, whichever comes first

- at least one troponin elevation of ≥ 50 times the upper limit of normal AND at least 20% of greater than the baseline troponin value, per the troponin Local Laboratory, within 48 hours following PCI or hospital discharge, whichever comes first.
- Co-secondary tests: (i) a short tirofiban regimen of a high-dose bolus plus a 1-2 hour infusion duration post procedure is non-inferior to a long tirofiban regimen of a high-dose bolus plus a 12-18 hour infusion, and (ii) a long tirofiban regimen of a high-dose bolus plus a 12-18 hour infusion is non-inferior to label-dosing eptifibatide with respect to the same secondary tests in the list above.

9.3.3 Safety Endpoints

- Nature, severity, and study drug relationship of all bleeding events
 - Specifically,
 - Bleeding events according to REPLACE-2 Major bleeding definition
 - Bleeding events according to TIMI Major bleeding definition
 - Bleeding events according to REPLACE-2 Minor bleeding definition
 - Bleeding events according to TIMI Minor bleeding definition
 - Bleeding events according to REPLACE-2 Plus Major bleeding definition
 - Bleeding events according to TIMI Plus Major bleeding definition
 - Sum of REPLACE-2 Major and Minor bleeding
 - Sum of REPLACE-2 Plus Major and Minor bleeding
 - Sum of TIMI Major and Minor bleeding
 - Sum of TIMI Plus Major and Minor bleeding
- Non-bleeding adverse events
- Change in lab parameters
 - Specifically,
 - Thrombocytopenia ($< 100,000$ cells/ μL)
 - Severe Thrombocytopenia ($< 50,000$ cells/ μL)
 - Profound Thrombocytopenia ($< 20,000$ cells/ μL)
- Length of hospital stay

9.3.4 Potential Covariates and/or Subgroups

- Patient with acute coronary syndromes
- STEMI > 48 hours
- Stable angina
- Troponin baseline negative
- Troponin baseline positive
- Femoral access PCI
- Radial access PCI
- Total stent length
- Use of a closure device
- Number of stents implanted
- Single vessel
- Multivessel
- Number of vessels treated
- Total infusion time

- Patients receiving P2Y₁₂ antagonist therapy between 24 and 6 hours prior to randomization
- Patients receiving P2Y₁₂ antagonist therapy between 6 and 1 hours prior to randomization
- Patients receiving P2Y₁₂ antagonist therapy between 1 hour prior to randomization and 15 minutes after completion of the PCI procedure
- Type 1 diabetes mellitus
- Type 2 diabetes mellitus
- Prior use of GPIIb/IIIa inhibitor therapy
- Indication for PCI
- Age < 65 years, ≥65 years and ≥75 years
- Sex
- Race
- Clopidogrel
- Prasugrel
- Ticagrelor
- Elective PCI
- Urgent PCI

9.4 Analysis Population

All efficacy analyses will be performed on the modified intent-to-treat population (MITT) (i.e. randomized patients who underwent PCI and received study drug) and on the per-protocol population (i.e. patients who completed the full course of the study without major protocol violations). Safety analyses will be performed on the safety population (i.e. patients who received any study treatment).

9.5 Sample Size Calculations

The primary outcome variable for this trial is the composite of death, PPM, uTVR or REPLACE-2 Major bleeding.

Sample size calculations ensure that the one-sided non-inferiority hypothesis of the first primary outcome can be tested with a type-I error rate of 2.5% and 99% power. An event rate of 32.5% will be assumed for the active control and test group which was then later assumed to be 51% based on pooled analysis after 159 randomized patients. A sample size re-estimation was conducted after 159 randomized patients.

For the two co-primary tests, a sample size of approximately 350 was obtained by setting the non-inferiority margin at 19.1%, power at 94.5% and a 1-sided alpha at 0.025 assuming an event rate of 51%.

For the secondary endpoints involving ≥10 times troponin and comparing short tirofiban to eptifibatide, a sample size of approximately 500 was obtained by setting the non-inferiority margin at 12.4%, power at 85% and a 1-sided alpha at 0.025 assuming an event rate of 32% (based on ≥10 times troponin elevation data from the 159 randomized patients).

SAS version 9.2 (SAS Institute, Cary, NC) was used for the sample-size calculations.

The trial may be terminated for futility at an interim point in time. Details of the methodology and stopping boundaries will be provided in the Statistical Analysis Plan.

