Physician-directed standard background therapies will include dual oral antiplatelet therapy with aspirin and an approved oral P2Y₁₂ antagonist as well as antithrombotic therapy with unfractionated heparin. Physician-directed P2Y₁₂ antagonist therapy and choice of femoral or radial access site must be pre-specified prior to randomization.

The first 159 patients were randomized to the following two treatment arms on a 1:1 basis:

1. Tirofiban (25 µg/kg bolus followed by a 0.15 µg/kg/min infusion for the duration of the PCI procedure plus a minimum of one hour and up to a maximum of two hours post-PCI).
2. Eptifibatide (180 µg/kg bolus followed by a 2.0 µg/kg/min infusion for 18 hours post-PCI [minimum 12 hours mandated], with a second 180 µg/kg bolus 10 min after the first).

The three treatment arms for enrollment after the 159th patient were:

1. Short Tirofiban (25 µg/kg bolus followed by a 0.15 µg/kg/min infusion for the duration of the PCI procedure plus a minimum of one hour and up to a maximum of two hours post-PCI).
2. Eptifibatide (180 µg/kg bolus followed by a 2.0 µg/kg/min infusion for 18 hours post-PCI [minimum 12 hours mandated], with a second 180 µg/kg bolus 10 min after the first).
3. Long Tirofiban (25 µg/kg bolus followed by a 0.15 µg/kg/min infusion for 18 hours post-PCI) [minimum 12 hours mandated].

Enrolment in the Long Tirofiban arm has been completed. Enrolment continues in the Short Tirofiban and Eptifibatide arms as outlined above.

SAMPLE SIZE: Approximately 550 patients will be enrolled in the trial. The rate of the primary composite endpoint is assumed to be 51% in both the eptifibatide and tirofiban treatment groups. The absolute margin for the difference between the eptifibatide and the short tirofiban group is set at 19.1%. A sample size of approximately 500 for the comparison between the short tirofiban and the eptifibatide group was obtained by setting a power at 99% and a 1-sided alpha at 0.025. For the second test, a sample size of approximately 350 for the comparison between the short tirofiban and the long tirofiban group was obtained by setting power at 94.5% and a 1-sided alpha at 0.025. For the third test, a sample size of approximately 350 for the comparison between the long tirofiban and the eptifibatide group was obtained by setting power at 94.5% and a 1-sided alpha at 0.025.

DOSAGE/DOSAGE FORM, ROUTE, AND DOSE REGIMEN

Aspirin:	As per local practice and physician discretion

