5.0 STUDY DESIGN

5.1 Summary of Study Design

A randomized, multicenter, open-label study comparing tirofiban I.V. bolus injection followed by a maintenance infusion for the duration of the PCI procedure plus a minimum of one hour and up to a maximum of two hours post-PCI versus label-dosing eptifibatide. Patients were randomized to tirofiban or eptifibatide using a 1:1 allocation ratio. At 159 randomized patients, a 1:1:1 randomization was initiated, randomizing patients to short tirofiban, eptifibatide or long tirofiban. Enrolment in the long tirofiban arm has been completed. Patients are mandated to stay a minimum of 18 hours following PCI.

Physician-directed standard background therapies will include dual oral antiplatelet therapy with aspirin and an approved oral P2Y₁₂ antagonist as well as antithrombotic therapy with unfractionated heparin. Physician-directed P2Y₁₂ antagonist therapy and choice of femoral or radial access site must be pre-specified prior to randomization.

The first 159 patients were randomized to the following two treatment arms on a 1:1 basis:

1. Tirofiban (25 µg/kg bolus followed by a 0.15 µg/kg/min infusion for the duration of the PCI procedure plus a minimum of one hour and up to a maximum of two hours post-PCI).
2. Eptifibatide (180 µg/kg bolus followed by a 2.0 µg/kg/min infusion for 18 hours post-PCI [minimum 12 hours mandated], with a second 180 µg/kg bolus 10 min after the first).

The three treatment arms for enrollment after the 159th patient were:

1. Short Tirofiban (25 µg/kg bolus followed by a 0.15 µg/kg/min infusion for the duration of the PCI procedure plus a minimum of one hour and up to a maximum of two hours post-PCI).
2. Eptifibatide (180 µg/kg bolus followed by a 2.0 µg/kg/min infusion for 18 hours post-PCI [minimum 12 hours mandated], with a second 180 µg/kg bolus 10 min after the first).
3. Long Tirofiban (25 µg/kg bolus followed by a 0.15 µg/kg/min infusion for 18 hours post-PCI) [minimum 12 hours mandated].

Subject enrolment in the Long Tirofiban arm has been completed. Enrolment continues in the Short Tirofiban and Eptifibatide arms as outlined above.

The short tirofiban versus eptifibatide comparison involves approximately 500 patients; the short tirofiban versus long tirofiban comparison involves approximately 350 patients; and the long tirofiban versus eptifibatide comparison involves approximately 350 patients. Approximately 550 patients will be enrolled into the study.

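### The 94.5% co-primary power at about 350 patients per pair assumes equal arms. The stated pair sizes imply 250:100, which gives about 90% and a total of 600 rather than 550.

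*Protocol*

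**What the plan says.** The Protocol synopsis states the total: "Approximately 550 patients will be enrolled in the trial". It then sizes the co-primary tests by pair. "For the second test, a sample size of approximately 350 for the comparison between the short tirofiban and the long tirofiban group" is given 94.5% power at one-sided alpha 0.025, and so is the last comparison: "For the third test, a sample size of approximately 350 for the comparison between the long tirofiban and the eptifibatide group". The first primary test is given about 500 patients and 99% power.

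Protocol 5.1 repeats the pair sizes: "The short tirofiban versus eptifibatide comparison involves approximately 500 patients; the short tirofiban versus long tirofiban comparison involves approximately 350 patients". It gives the remaining pair, long tirofiban against eptifibatide, the same size of about 350. The same section repeats the total of about 550. Protocol 9.5 describes the co-primary calculation: "a sample size of approximately 350 was obtained by setting the non-inferiority margin at 19.1%, power at 94.5" per cent, at an event rate of 51%. SAP 2.4 and 2.6 carry the same sizes and powers.

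Protocol 9.1 gives the allocation history. "The first 159 patients were randomized to the following two treatment arms on a 1:1 basis", namely short tirofiban and eptifibatide. "After 159 patients were randomized, a 1:1:1 randomization was initiated, randomizing patients to short tirofiban, eptifibatide or long tirofiban". Randomization to the long arm then finished and the ratio went back to 1:1. SAP 2.5 also says that long-arm enrolment is complete. Neither document gives an n per arm or the allocation ratio behind the 94.5%.

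**The concern.** For a fixed pair total, power falls as the split becomes less equal. Long tirofiban received nobody in the first period, and nobody in the third, so it should be well below the other two arms. Both co-primary comparisons use that arm, yet their stated power looks like an equal-arm figure.

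The sizes also do not add up. Each patient belongs to two of the three pairs, so the pair sizes should sum to twice the total. They do not.

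Two of the three primary hypotheses are affected. If type II error is nearer 10% than 5.5%, a failure to show non-inferiority in a long-tirofiban comparison is harder to interpret than the protocol suggests.

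**Working it through.** **Inputs.** Event rate p = 0.51 in both arms (synopsis; Protocol 9.5). Margin d = 0.191 for all three tests (Protocol 9.2). One-sided alpha 0.025, so z = 1.96.

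**Formula.** Power = Φ( d / √[p(1−p)(1/n1 + 1/n2)] − 1.96 ).

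**1. Reproduce the plan's figures at 1:1.**
- 174:174: SE = √[0.2499 × 2/174] = 0.0536; 0.191/0.0536 = 3.564; Φ(1.604) = 94.6%. The stated 94.5% at about 350 is reproduced.
- 250:250: SE = 0.0447; Φ(2.312) = 99.0%. The stated 99% at about 500 is reproduced.
- A pair of exactly 350 reaches 94.5% only if the smaller arm has at least 159 (191:159).

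**2. Solve for the arms.** With S = short tirofiban, E = eptifibatide and L = long tirofiban: S+E = 500, S+L = 350, E+L = 350. The sum of the pairs is 1,200, so the total is 1,200/2 = 600. Hence L = 600 − 500 = 100 and S = E = 250. The stated total is 550.

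**3. Power at those arms.** 250:100: SE = √[0.2499 × (1/250 + 1/100)] = 0.0591; 0.191/0.0591 = 3.229; Φ(1.269) = 89.8%. Simulating the SAP 3.10.1 decision rule with a Wald one-sided 97.5% interval (assumed, since the SAP does not name the interval) gives about 90.0%. The shortfall does not come from the formula.

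**4. What the allocation history allows.** The first 159 patients add 79.5 on average to each of S and E and none to L. The 1:1:1 period adds equally to all three arms, and the last period adds only to S and E. So the expected S = E is at least L + 79.5.
- Best split of a 350 pair: L + (L + 79.5) = 350, so about 215:135, power 93.6%.
- Best split of a total of 550: L = (550 − 159)/3 = 130.3 and S = E = 209.8, power 92.9%; the first comparison is then about 420.
- Under the same constraint, 94.5% is first reached at a total of 588 (223/223/142), with a first comparison of 446.

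**5. Co-primary power under different reconciliations.**

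| Held fixed | S/E/L | Total | Power |
|---|---|---|---|
| 500, 350, 350 | 250/250/100 | 600 | 89.8% |
| 500 and 550 | 250/250/50 | 550 | 69.4% |
| 550, with L = 100 assumed | 225/225/100 | 550 | 88.9% |
| 550, most balanced expected split | 210/210/130 | 550 | about 93% |
| 350, 350 and 550 | 200/200/150 | 550 | 94.3% |

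The last row comes closest to the stated power, but its first comparison is 400 (96.9%, not 99%) and its arm gap of 50 does not fit the expected gap of about 80.

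**6. Effect on the other stated powers.** The secondary endpoints at ≥10 times the upper limit of normal use p = 0.32, d = 0.124 and a stated 85%.

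| S:E | First primary test | ≥10× secondary |
|---|---|---|
| 250:250 | 99.0% | 84.4% |
| 225:225 | 98.2% | 80.5% |
| 210:210 | 97.5% | about 78% |

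**The case against.** The strongest reply is that no calculation is wrong. Section 9.5 describes a planning calculation, and it reproduces at 1:1. On this view the defect is an unstated ratio and missing arm sizes, which is incomplete reporting. It is also true that every size is approximate. If figures are rounded to the nearest 50 (an assumption), 238/238/98 fits all four: pairs of 476, 336 and 336, total 574. The literal total of 600 should therefore not be pressed too hard. And if 550 is the firm number and the split is the most balanced one expected, the loss is only about 1.6 points.

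Much of this stands. The documents do not show which figure is loose, the shortfall may be small, and the 69.4% case is an extreme because it makes the co-primary pairs 300 rather than 350.

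It does not rescue the stated power. With S = E, every split that fits all four sizes gives 83% to 89% under nearest-50 rounding, or 87% to 90% if each size may be off by 5%. The 1:1 assumption behind 94.5% was already untrue of the design when these sections were written, because they themselves record the unequal allocation.

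**Conclusion.** The concern holds. The 94.5% is an equal-arm figure attached to comparisons that the design makes unequal. At the stated pair sizes the power is 89.8%, so type II error is about 10% instead of 5.5%, and the implied total exceeds the stated one by 50 patients (9%). At a pair of 350, the best split expected from the allocation history gives 93.6%.

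This rests on the plan's own 51% rate and 19.1-point margin, no true difference between arms, equal short-tirofiban and eptifibatide arms, and expected rather than actual allocation counts. The size of the shortfall is uncertain because the arm sizes are not given.

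The consequence is limited. Type I error, the margin and the decision rule in SAP 3.10.1 are untouched, and the reported interval will show the precision actually achieved. It should be fixed, but it does not threaten the validity of the analysis.

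**What to change.** State the actual number randomized to long tirofiban, which is known because enrolment in that arm is complete, and the planned numbers for short tirofiban and eptifibatide. Make the three pair sizes and the total agree with those numbers. Label 350 and 94.5% as a 1:1 planning figure, and give the power at the actual split beside it (about 90% if it is 250:100). Recheck the 99% and 85% figures against the same arm sizes. The places to amend are the Protocol synopsis and Sections 5.1, 9.1 and 9.5, and SAP 2.4 and 2.6.

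The cost is wording only, with no extra patients and no change to the analysis. The stated co-primary power becomes about 5 points less favourable if the split is 250:100, and less than that if the long arm is larger.
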